9.2.5 Adverse Events

AEs will be recorded from the Screening Visit until the Follow-up/Early Termination Visit (30 days after the last dose of study medication for serious AEs). In order to avoid bias in eliciting AEs, subjects should be asked a non-leading question, such as “How are you feeling?”

All AEs will be recorded on the appropriate pages in the eCRF and in source documents. Appropriate follow-up will be required for any AEs ongoing at study exit.

Definitions and reporting procedures are described in [Section 10](#).

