Safety will be monitored throughout the study with routine safety assessments (AE recording; vital signs; 12-lead ECG; clinical laboratory tests). A physical examination will be conducted at screen and follow-up. Additional safety assessments will be done at any time as considered appropriate by the Investigator. Additional safety assessments not specified in the protocol may be performed as required by Quotient Sciences Standard Operating Procedures, but these will not be entered into the eCRF. Any abnormal assessments observed during non-protocol required safety assessments will be recorded as AEs if appropriate and the corresponding abnormal assessment entered as an unscheduled assessment in the eCRF.

Subjects will have a final outpatient follow-up visit two weeks following the final dose of study medication. At this visit the subject will be asked when their next menstrual cycle started (the cycle after the completion of dosing).

An overview of the study is shown in [Figure 6-1](#).

Figure 6-1: Study Schematic

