8.8.2 Contraception

All subjects must agree to use two acceptable methods of birth control for the duration of participation in the study and 30 days after the last dose, one of which must be a barrier method with spermicide.

Acceptable methods of birth control are:

- Surgical sterilization of the subject's male partner (vasectomy with documented azoospermia), if he is the sole partner of that subject;
- A non-hormonal intrauterine device (IUD) with failure rate of less than 1% per year inserted by qualified physician at least one month before study drug administration and to remain in place for at least 30 days after the last dose of study drug;
- Barrier methods such as male condom or cap, diaphragm or sponge with spermicide

Women who lead either an abstinent or an exclusively homosexual lifestyle are not required to use two methods of contraception but are required to commit to this lifestyle for the duration of the study and 30 days after the last dose.

Hormonal contraceptives are not acceptable by any route (systemic, implants, depot, intrauterine).

Serum pregnancy tests will be done on women of child-bearing potential at screening and on Day 21 or 22 of Cycle 1, and a urine pregnancy test performed on Day 1 or 2 of Cycle 2 (prior to the first dose of study medication). All tests must be negative for the subject to continue in the study.

A final serum pregnancy test will be done at the final follow up visit.

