9 STUDY ASSESSMENTS AND PROCEDURES

Please see [Table 9-1](#) for the complete schedule of assessments. [Section 9.6](#) summarizes the order of procedures when more than one activity is scheduled for the same time point and permissible time windows.

Table 9-1 Schedule of Events

Day	Screening	Cycle 1					Cycle 2					Follow-up
	-21 ^a	1	3/4	9/10	15/16	21/22	1/2	3/4	9/10	15/16	21/22	35-38
Clinic visit (out-patient)	X		X	X	X	X	X					X ^e
Informed consent	X ^b											
Menstrual flow starts		X					X ^l					
Record dates of start of menstruation		X										X
Medical History	X											
Physical examination	X											X
Vital signs ^c	X					X	X ^f	X ^h	X ^h	X ^h	X	X
Oral or aural body temperature	X						X ^f					X
12-lead ECG	X					X	X ^f	X ^h	X ^h	X ^h	X	X
Weight	X					X	X					X
Serology ^d	X											
Drugs of abuse screen	X					X	X ^f					
Hematology and Clinical Chemistry	X					X	X		X		X	X
Serum pregnancy test	X					X						X
Urine pregnancy test							X ^f					
Sample for PD hormone assessment			X	X	X	X		X ^{h,i}	X ^{h,i}	X ^{h,i}	X ⁱ	
Sample for PK								X ^{h,j}	X ^{h,j}	X ^{h,j}	X ^j	
Randomization						X						
NT-814/placebo once daily							X					X ^g
Adverse Event / con med reporting ^k	X											X

- a Screening to be scheduled within 21 days of the anticipated start of the next menstrual cycle. This period can be extended if the menstrual period starts later than anticipated.
- b Informed consent can be obtained prior to the screening visit. The screening period starts from the date of the screening procedures, not from the date of consent.
- c Vital signs: systolic and diastolic blood pressure, pulse
- d Hepatitis B surface antigen, hepatitis B core antibody, hepatitis C antibody, human immunodeficiency virus
- e Daily clinic visits in the morning, starting on Day 1 or 2 of Cycle 2 and ending on Day 21/22.
- f Performed prior to the first dose
- g Doses administered in the morning, in the clinic ~1-2 hours after breakfast; starting on Day 1 or 2 of Cycle 2; last dose will be day prior to clinic visit on Day 21/22. Doses to be administered at the same time each day (±1hr).
- h Prior to administration of dose on the days shown
- i PD sample days must be the same relative to Day 1 on both Cycles 1 and 2
- j PK samples taken on same day/time as PD samples in Cycle 2
- k AEs and concomitant medication to be reported from the start of screening
- l Requires visual verification

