10.2 Pregnancy

Female subjects will be instructed that they should report to the Investigator if, despite the measures in place to prevent pregnancy, they become pregnant during the study or within 30 days after their last dose of IMP, including any pregnancy occurring during the study but confirmed after completion of the study.

Any female subject reporting a pregnancy during the study will be withdrawn from the study immediately; no further IMP may be administered.

In the event that a subject becomes pregnant during or within 30 days after the end of the study, the Investigator will collect and record information on that pregnancy on the appropriate form and submit it to Emas within 24 hours of learning of a subject's pregnancy through the same process as reporting an SAE. The subject will also be followed to determine the outcome of the pregnancy. Information on the status of the mother and child will be forwarded to the Emas. Generally, follow-up will be no longer than six to eight weeks following the estimated delivery date. Any premature termination of the pregnancy will be reported.

Pregnancy itself is not considered an AE. However, any pregnancy complication, spontaneous or elective abortion for medical reasons, still birth, neonatal death, or congenital anomaly will be recorded as an AE or SAE as applicable.

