12 END OF THE STUDY

The end of the study is defined as the date of last contact (visit, telephone call, email, etc) with any study subject.

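### About half of the 30-day post-dose window for serious adverse events and pregnancy has no scheduled contact; separately, Section 10.2 dates the pregnancy window from two different anchors

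*Protocol*

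**What the plan says.** **Serious adverse events.** Protocol Section 9.2.5 separates the two kinds of event: adverse events are recorded "until the Follow-up/Early Termination Visit (30 days after the last dose of study medication for serious AEs"). It asks for a non-leading question to elicit events, and for follow-up of events still open when the subject leaves the study.

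**Last scheduled contact.** Section 6 states: "Subjects will have a final outpatient follow-up visit two weeks following the final dose of study medication". The follow-up column of Table 9-1 is Day 35-38 and is the last column. Footnote g of that table fixes the end of dosing: "last dose will be day prior to clinic visit on Day 21/22".

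**Pregnancy.** Section 8.8.2 requires contraception for 30 days after the last dose and adds: "A final serum pregnancy test will be done at the final follow up visit". Under Section 10.2, subjects are told to report to the investigator if "they become pregnant during the study or within 30 days after their last dose of IMP". Further on, the same section sets out what the investigator collects: "In the event that a subject becomes pregnant during or within 30 days after the end of the study". Section 12 supplies the anchor for that second sentence: "The end of the study is defined as the date of last contact" with any subject, which is a date for the whole trial.

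**The concern.** A recording window that outlasts the last planned contact works only if someone tells the site about late events. For pregnancy the protocol gives subjects that instruction. For new serious adverse events it gives none. The non-leading question of Section 9.2.5 has no scheduled occasion after Day 35-38. The follow-up of open events covers only what is already known. The 24-hour reporting clock of Section 10.1.4 starts only when the investigator has determined that an event is serious.

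All subjects are pre-menopausal women on non-hormonal contraception, and Section 4.5.1 says that effects on the fetus have not been fully evaluated. At stake is the completeness of late safety data, and whether a report of no late events reflects questions asked or merely silence.

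The wording of Section 10.2 is a separate matter. It does not cause the gap in contact, but it leaves the site with two closing dates for collecting pregnancies.

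**Working it through.** **Inputs.** Last dose on Day 20 or 21 of Cycle 2 (Table 9-1, footnote g: the day before the Day 21/22 visit). Follow-up on Day 35 to 38 (Table 9-1). Window of 30 days after the last dose (Sections 9.2.5 and 10.2).

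**Step 1: interval to the last scheduled contact.** Interval = follow-up day − last-dose day. Days without scheduled contact = 30 − interval. Share = that remainder ÷ 30.

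| Last dose | Follow-up | Interval (days) | Days left of 30 | Share |
|---|---|---|---|---|
| Day 20 | Day 35 | 15 | 15 | 50% |
| Day 20 | Day 38 | 18 | 12 | 40% |
| Day 21 | Day 35 | 14 | 16 | 53% |
| Day 21 | Day 38 | 17 | 13 | 43% |

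The two weeks given in Section 6 are reproduced as the lower end of the 14-18 day range. The stretch without scheduled contact is 12-16 days, or 40-53% of the window.

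This holds for completers only. Section 7.4 asks withdrawn subjects to consent to a follow-up examination but does not time it from their last dose, so no figure can be given for early stoppers.

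**Step 2: how far apart the two pregnancy windows are.** Let E be the days from a subject's last dose to the end of the study.

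- *End of study read as each subject's own last visit, in both sentences.* E = 14 to 18. The subject's window closes at day 30 and the investigator's at E + 30 = 44 to 48. Difference: 14-18 days.
- *End of study read at trial level, as Section 12 defines it, in both sentences.* The subject's window covers the study or 30 days after the last dose, so it closes at the later of E and 30. The investigator's closes at E + 30. Difference = E + 30 − max(E, 30) = min(E, 30). With E of at least 14 for a completer, this is 14 to 30 days.

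Under either consistent reading the difference is about 14-30 days, and the investigator's window contains the subject's.

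**Step 3: effect of a contact at day 30.** The last subject's final contact moves from day 14-18 to day 30 after her last dose, which is 12-16 days later. If Section 10.2 stayed as it is, the investigator's window would move with it, to at least day 30 + 30 = 60. The two changes therefore belong together.

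**The case against.** The strongest reply is that Section 9.2.5 deliberately sets a longer period for serious events than for other adverse events. A recording period is a reporting duty, and nothing says it must be discharged at a planned visit. On this view an active call is a design preference. That is fair: the timing is not an internal contradiction, and the contact is proposed as an inexpensive improvement. The protocol still does not say how a new serious event after follow-up would come to the site's notice.

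The reply also has force on risk. The longest half-life in Section 4.3.1 is 22 hours, so 14 days is 14 × 24 ÷ 22 = 15.3 half-lives and little drug should remain at follow-up. Two contraceptive methods are required to day 30 (apart from women with an abstinent or exclusively homosexual lifestyle). Subjects are asked at follow-up when their next cycle began. Section 9.6 lets the investigator add visits for safety. All of this lowers the expected number of late events. It does not alter the fact that the protocol itself chose 30 days.

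Three stronger readings are tempting and are not supported:

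- *The second half of the window goes unobserved.* It lacks scheduled contact, but Section 10.2 tells subjects to report pregnancies, including those confirmed after completion, and events open at exit are followed.
- *The two pregnancy windows could differ by 12 weeks or more for Cohort 1.* That needs the word study to mean one subject's participation in one sentence and the whole trial in the other.
- *The final serum test would miss conceptions after a delayed ovulation.* Section 4.1 describes delayed ovulation with other compounds. The protocol gives no ovulation timing for NT-814 and no detection time for the test.

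**Conclusion.** The point holds as a gap in active ascertainment. For completers, 12-16 of the 30 days (40-53%) follow the last scheduled contact and the last pregnancy test. Over those days pregnancy depends on self-report, and no means of ascertaining new serious adverse events is stated.

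The two anchors in Section 10.2 are a drafting inconsistency of about 14-30 days. A reader might infer that pregnancies are lost between the two windows. They are not, because the investigator's is the wider and contains the subject's. On its own this would be a minor wording matter.

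The figures assume that dosing ends and follow-up takes place as Table 9-1 states, and that the end of the study is read the same way in both sentences. The statement about serious events is limited to the protocol. The participant information, which is not at hand, may tell volunteers to report late events. The effect is on the completeness of late safety data; the primary hormone analysis is untouched.

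**What to change.** Add to Table 9-1 one telephone or email contact at or after 30 days from each subject's own last dose, including subjects who stop dosing early, asking about serious adverse events and pregnancy. Refer to it in Section 9.2.5 as the means by which the serious-event window is closed. In Section 10.2, reconcile the two windows to a single one with a subject-level anchor, used for both the subject's reporting and the investigator's collection. Whether and when any further pregnancy test is done is for the sponsor and investigator to decide.

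The cost is one short remote contact per treated subject by existing site staff (up to 42 subjects plus at most 10 replacements, so no more than 52) and a few lines of text. Section 12 already counts telephone and email as contact. The downside is that the last subject's end of study moves 12-16 days later, about two weeks.

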9.2.6 Clinical Laboratory Safety Assessments

Blood and urine samples will be collected at the time points shown in [Table 9-1](#) for clinical laboratory safety assessments listed in [Table 9-2](#).

Table 9-2 Clinical Laboratory Safety Tests

Chemistry	
Alanine aminotransferase	Creatine kinase
Albumin	Creatinine
Alkaline phosphatase	Glucose
Aspartate aminotransferase	Gamma-glutamyltransferase
Bicarbonate	Magnesium
Bilirubin (total)	Phosphate (inorganic)
Blood urea nitrogen/urea	Potassium
Calcium	Sodium
Chloride	Total protein
Hematology	
Hemoglobin	Mean corpuscular hemoglobin concentration
Hematocrit	Mean corpuscular hemoglobin
Red blood cell count	White blood cell count with differential
Mean corpuscular volume	Platelets
Urinalysis	
Bilirubin	Nitrite
Blood	pH
Glucose	Protein
Ketones	Specific gravity
Leukocyte esterase	Urobilinogen
Microscopic examination (if urine protein, blood, nitrite, or leukocyte esterase values are out of range)	
Other	
Urine for drugs of abuse, including opiates (including methadone); cocaine; amphetamines; methamphetamines; cannabinoids; barbiturates; and benzodiazepines	
Serology: hepatitis B surface antigen (HBsAg), hepatitis B core antibody (anti-HBc), hepatitis C (HCV) antibody, human immunodeficiency virus (HIV)	
Serum/ urine pregnancy test	

Samples will be collected and handled in accordance with the analytical laboratory's standard procedures. The analytical laboratory will perform blood safety tests and urinalysis using instruments interfaced to a validated general laboratory information management system.

All laboratory test reports must be reviewed, signed and dated by the Investigator or a medically-qualified designee, and filed with the subject's medical record. The Investigator will comment on all results outside the local reference range and determine whether they are clinically significant. Clinically significant findings must also be reported as AEs in the eCRF.

A positive result in any serology parameter will exclude the subject from participation in the study. Pregnancy tests must be negative for the subject to enter or continue in the study. Any pregnancy should be reported as detailed in [Section 10.2](#).

9.3 Pharmacodynamic (Hormone) Assessments

Blood samples will be collected at the time points shown in [Table 9-1](#) for assessment of serum LH, FSH, estradiol and progesterone.

Samples for assessment of estradiol and progesterone will be analyzed using an ultrasensitive liquid chromatography – mass spectrometry (LC-MS/MS) assay. LH and FSH will be analyzed by immunoassay.

Samples will be collected and handled in accordance with the analytical laboratory's standard procedures. The analytical laboratory will perform hormone tests using instruments interfaced to a validated general laboratory information management system.

9.4 Pharmacokinetics

9.4.1 Sample Collection and Handling

Blood samples will be collected at the time points shown in [Table 9-1](#) for assay for plasma concentration of NT-814.

9.4.2 Analytical Procedures

Plasma samples will be analyzed to determine concentrations of NT-814 at Aptuit Srl, Verona, Italy, using the current Sponsor-approved validated analytical methodology. Raw data will be stored in the Good Laboratory Practice archive of Aptuit.

Plasma concentration data will be transferred to Quotient, which will be responsible for generating the relevant tables and listings.

9.4.3 Pharmacokinetic Analysis

Formal pharmacokinetic analyses will not be performed.

9.5 Volume of Blood Sampling

Table 9-3 shows the estimated total blood volume requirements for the study.

Table 9-3 Estimated Blood Sample Volume Requirements

	Volume per sample mL	Number of samples	Total Volume mL
Serology	3.5	1	3.5
Hematology	3	3	9
Biochemistry	3.5	3	10.5
Sample for PD (hormones)	10	8	80
Samples for PK	4	4	16
TOTAL VOLUME			119 mL

The volume required for safety samples may vary accordingly to local laboratory requirements. However, the total volume is not expected to exceed 350 mL per subject.

9.6 Priority Order of Study Assessments; Permitted Windows

Note the following with regard to sequence of tests and acceptable time windows.

- Informed consent can be obtained before the actual screening visit, with the 21-day screening period starting from the date of the screening visit and not the date consent is obtained
- Predose procedures on Day 1 or 2 of Cycle 2 must be completed before the first dose
- Assessments on Cycle 2 Days 3 or 4, 9 or 10, and 15 or 16 should be performed prior to dosing
- As far as possible, each subject should be dosed at the same time of day during the dosing period in Cycle 2; however, a window of ± 1 hr is permitted
- The serum hormone sampling days relative to Day 1 of Cycle 2 will match the days samples were taken in Cycle 1 (relative to Day 1 of Cycle 1) within each subject (e.g. if the subject attended the clinic on Day 4 in Cycle 1, the hormone sample must be taken on Day 4 in Cycle 2; if they attended on Day 9 in Cycle 1 the hormone sample must be taken on Day 9 in Cycle 2, and so on).
- Collection of samples for hormone assessment should be performed at approximately the same time of day throughout Cycles 1 and 2; however, a window of ± 1 hr is permitted
- Measurement of vital signs and ECG recordings should be avoided within 15 minutes after venipuncture and, therefore, should normally be done before blood sampling.

The Investigator may repeat tests, conduct tests other than those specified, and schedule additional visits in the event of a technical failure and/or if extra observations or samples of blood or urine are needed to monitor subject safety. These will not be considered protocol deviations.

Any deviation outside these permitted windows must be noted in the subject's clinic chart and eCRF.

10 ADVERSE EVENTS AND PREGNANCY

10.1 Adverse Events

10.1.1 Definitions

An **Adverse Event (AE)** is any untoward medical occurrence in a patient or clinical trial subject administered a medicinal product and which does not necessarily have a causal relationship with this treatment. An AE can therefore be any unfavorable and unintended sign (including an abnormal laboratory finding, for example), symptom, or disease, temporally associated with the use of a medicinal product, whether or not considered related to the medicinal product.

Adverse Drug Reaction (ADR): all events considered untoward and unintended responses to a medicinal product related to any dose should be considered adverse drug reactions. The definition also covers medication errors and uses outside what is foreseen in the protocol, including misuse and abuse of the product. The phrase ‘responses to a medicinal product’ means that a causal relationship between a medicinal product and an adverse event is at least a reasonable possibility, i.e., a relationship cannot be ruled out.

Serious Adverse Event (SAE)

An adverse event that, at any dose:

- Results in death
- Is life-threatening (i.e., the subject was at risk of death at the time of the event; it does not refer to an event which hypothetically might have caused death if it was more severe)
- Requires inpatient hospitalization or prolongation of existing hospitalization

Hospitalizations are defined as initial or prolonged admissions that include an overnight stay. Attendance at an Emergency Room that extends overnight but does not result in formal admission is not considered an overnight stay. Hospitalization or prolonged hospitalization for technical, practical or social reasons, in the absence of an adverse event is also not an SAE.

- Results in persistent or significant disability/incapacity
- Is a congenital anomaly/birth defect
- Is considered to be an important medical event

Based upon medical and scientific judgment, important medical events that may not be immediately life-threatening, or result in death or hospitalization, but may jeopardize the subject and may require intervention to prevent one of the other outcomes listed in the definition above may be considered an SAE.

Unexpected Adverse Drug Reaction

An adverse reaction, the nature or severity of which is not consistent with applicable reference safety information in the IB.

Reports that add significant information on the specificity, increase of occurrence, or severity of a known, already documented serious adverse reaction constitute unexpected events.

Suspected Unexpected Serious Adverse Reaction (SUSAR)

An SAE that is suspected to be related to the administered medicinal product, and the nature or severity of which is not consistent with applicable reference safety information.

